1.0 HYPOTHESIS AND STUDY OBJECTIVES

1.1 Hypotheses:

- 1.1.1 HCV is additive with HIV in promoting CVD risk through increased immune activation and inflammation.
- 1.1.2 Markers of endothelial function, inflammation, and thrombosis that are not produced by the liver will provide more accurate and novel biomarkers for assessment of CVD risk in HIV/HCV coinfecting persons.
- 1.1.3 Treatment of HCV in HIV/HCV coinfecting persons will improve endothelial function and reduce chronic immune activation and inflammation.

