2.0 INTRODUCTION

2.1 Background

Hepatitis C virus (HCV) infection is a leading cause of morbidity and mortality among those with HIV-1. Non-liver related morbidity and mortality, including cardiovascular outcomes, are poorly characterized in HIV/HCV coinfection. All-cause mortality is increased in HIV patients with HCV coinfection, independent of HIV disease progression.¹ Not only liver-related, but non-liver related deaths may be reduced with HCV treatment.^{2,3} However, non-liver related outcomes in HIV/HCV coinfection remain poorly characterized. Large retrospective observational studies have suggested an increased risk of CVD events in HCV-infected individuals, both with and without HIV infection.⁴⁻⁶ The contribution of HCV to elevated CVD risk in HIV patients is unknown. Multiple potential mechanisms for increased CVD risk with HCV infection exist, including hepatic steatosis, insulin resistance, and diabetes mellitus.^{7,8} Chronic immune activation, implicated in HIV-associated accelerated atherosclerosis, is further increased with HCV coinfection.^{9,10}

Endothelial function, a predictor of CVD risk, has not been adequately characterized in HIV/HCV coinfection. Endothelial dysfunction mediates development and progression of atherosclerosis.¹¹ HIV-infected patients have impaired endothelial function compared to non-HIV-infected patients.¹² In a single small cross-sectional analysis by Masia et al, no difference was seen in endothelial function measured by brachial flow-mediated dilation (FMD) in HIV/HCV coinfecting versus HIV monoinfected persons, but interpretation of their findings is limited by confounding related to inconsistent HIV suppression, which has a clear impact on these measures.¹³ Peripheral arterial tonometry (PAT) is an established, non-invasive method for assessment of endothelial function that has been shown to both correlate with known CVD risk factors and predict CVD risk in multiple non-HIV infected populations.¹⁴⁻¹⁶ Its characteristics of reproducibility and reduced inter-operator variability in comparison to FMD make it an attractive tool for the assessment of CVD risk in HIV-infected persons.¹⁷

Routine CVD risk markers are altered with HCV infection and non-hepatically produced markers of endothelial dysfunction and inflammation may be better predictors of CVD risk in this patient population. Lipid and hsCRP levels are widely used for CVD risk

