6.3.7 Concomitant Medications

Initiation and discontinuation of all concomitant medications should be recorded on the CRF with start and stop dates. All ART (including interruption of ART for at least 7 days), HCV treatment (approved or experimental), immune-based and

anti-inflammatory therapy, prescription drugs, vaccines, alternative therapies, dietary supplements, and any experimental therapies taken daily for at least 7 days must be recorded. Changes only in dose or formulation do not need to be recorded.

At the premature study discontinuation visit, record all concomitant medications and ART per above guidelines, including ongoing medications.

6.3.8 Laboratory Evaluations (Note: the majority of these will be collected from the medical records and will not be drawn for the study)

The following must be recorded on CRFs and keyed into the database **unless otherwise indicated**:

Hematology

Hemoglobin, hematocrit, white blood cell count (WBC), absolute neutrophil count (ANC), and platelets within 120 days prior to study entry and **within 120 days prior to the week 52/study discontinuation visit**.

Chemistry

Sodium, potassium, chloride, bicarbonate, blood urea nitrogen (BUN), creatinine, and glucose within 120 days prior to study entry and **within 120 days prior to the week 52/study discontinuation visit**.

Liver Function Tests

Total bilirubin, indirect bilirubin, direct bilirubin, aspartate aminotransferase (AST), alanine aminotransferase (ALT), and alkaline phosphatase, and albumin within 120 days prior to study entry and **within 120 days prior to the week 52/study discontinuation visit**.

INR

INR obtained at a local laboratory within 120 days prior to study and **within 120 days prior to the week 52/study discontinuation visit**.

Pregnancy Test

For women with reproductive potential: Serum or urine beta-human chorionic gonadotropin (β -HCG [urine test must have a sensitivity of at least 50 mIU/mL]) within 28 days prior to study entry and at week 52/study discontinuation visit.

Hepatitis C Antibody Test

For HIV-monoinfected subjects only, screening HCV antibody within 1 year prior to study entry and within 120 days prior to the week 52/study discontinuation visit.

Hemoglobin A1c

For diabetic subjects only, hemoglobin A1c obtained within 180 days prior to study entry and within 120 days prior to the week 52/study discontinuation visit.

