9.3 Sample Size and Accrual

9.3.1 The primary comparison is of baseline RHI between the HIV/HCV coinfecting and HIV monoinfected groups. The estimated difference in RHI between the 2 groups is assumed to be the difference between high-risk CVD (HIV/HCV) and moderate-risk CVD (HIV). RHI is expected then to be 1.6 in HIV/HCV and 1.3 in HIV, with standard deviation (SD) of 0.37.⁵² With a sample size of 80 HIV/HCV and 40 HIV, we have an estimated power of 99% for detection of the expected difference in RHI between the HIV/HCV and HIV groups. However, if we conservatively estimate the difference in baseline RHI to be 0.2 between the 2 groups, we will have 80% power with this sample size. For select secondary analyses of differences in the CVD biomarkers of sICAM-1 (expected difference of 779 vs 1284 ng/mL, SD=526) and sE-selectin (118 vs 223 ng/mL, SD=190),³⁰ we will have 99% and 81% power, respectively, with this sample size.

Accrual of about 20 subjects per month is expected, to complete enrollment in 6 months.

9.3.2 With 80 HCV/HIV subjects, we will have 80% power to detect a correlation between any one marker and RHI of > 0.31 . With 40 HIV subjects, we will have 80% power to detect a correlation > 0.42 , correlations that have been seen in other populations.^{53,54}

9.3.3 Among 80 HIV/HCV subjects, we expect about 40 (50%) will initiate HCV treatment. Out of 40 who initiate HCV treatment, we expect about 27 (67%) will be responders and 13 will be non-responders. To compare responders (n=27) with subjects without treatment (n=40), we will have 80% power to detect a difference of 0.7 in effect size. To compare HIV monoinfected controls (n=40)

and untreated HIV/HCV subjects, we will have 80% power to detect a difference of 0.63 in effect size.

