9.4 Data Analysis Plan

9.4.1 Objective: To determine the effect of HCV coinfection on endothelial function in the HIV-1-infected cohort at baseline.

Descriptive statistics, including mean, SD, median, minimum, maximum, and interquartile range, will be provided for the overall cohort, by HCV status, and by PAT performance site for baseline patient characteristics, RHI, CVD biomarkers, HOMA-IR, hemoglobin A1c, and FRS. Histograms and scatter plots will be produced to visually inspect the distributions and pairwise association. Log-transformation as necessary will be done for RHI, if its distribution is found to be skewed. ANOVA (analysis of variance) will be used to compare continuous variables by HCV status and site and Chi-square test will be used to compare categorical variables. All tests will be 2-sided and a p-value less than 0.05 will be considered statistically significant.

Two sample t-test or Wilcoxon rank sum will be performed to compare RHI in the HIV/HCV vs HIV groups. Multiple linear regression analysis will also be carried out to compare RHI in HIV/HCV vs HIV, adjusting for PAT performance site and any differences in baseline characteristics including CD4 nadir and ART type. Subgroup analyses by race/ethnicity and gender will be conducted. Similar analyses will be carried out to compare biomarkers between the HIV/HCV and HIV groups. Given multiple comparisons, in addition to unadjusted p-values, we will report significance according to Benjamini-Hochberg false discovery rate method.⁵⁵

9.4.2 Objective: To assess whether non-hepatic biomarkers of endothelial dysfunction, inflammation, and thrombosis (sICAM-1, sE-selectin, Lp-PLA2, IL-6, and D-dimer) are better correlates of endothelial function than traditional hepatic-derived biomarkers (hsCRP and lipids) in HIV/HCV-coinfected in cross-sectional assessment.

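### The open covariate rule in the adjusted baseline RHI regression (Section 9.4.1) can admit consequences of HCV, so that model need not estimate the total effect of coinfection

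*Combined protocol and SAP*

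**What the plan says.** Section 9.4.1 addresses objective 1.2.2, the effect of HCV coinfection on baseline endothelial function. It plans an unadjusted two-sample t-test or Wilcoxon test of RHI. It then adds a multiple linear regression "adjusting for PAT performance site and any differences in baseline characteristics including CD4 nadir and ART type". No criterion for a difference is given. The same section compares variables by HCV status with ANOVA or chi-square tests and sets this threshold: "All tests will be 2-sided and a p-value less than 0.05 will be considered statistically significant".

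The protocol describes how HCV is thought to act. Section 1.1.1 states that "HCV is additive with HIV in promoting CVD risk through increased immune activation and inflammation". Section 2.1 Background adds: "Multiple potential mechanisms for increased CVD risk with HCV infection exist, including hepatic steatosis, insulin resistance, and diabetes mellitus".

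Section 6.3.8 collects haematology, including platelets, and liver tests for the baseline period: "aspartate aminotransferase (AST), alanine aminotransferase (ALT), and alkaline phosphatase, and albumin within 120 days prior to study entry". Section 3.0 frequency-matches the groups on age, race, sex, diabetes, smoking, statin and hormonal therapy use, and CD4 count.

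Section 9.4.1 extends the same approach to the biomarker comparisons. Section 9.4.2 reuses the Aim 1 covariates, which it calls confounders.

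**The concern.** A rule that admits a covariate because it differs by HCV status cannot tell a cause of the difference from a result of it. Group A must have chronic viremic HCV, in place before the baseline measurements. The factors most naturally regarded as confounders are largely matched, and so should tend not to differ. Liver tests and platelets are not matched, and they are among the variables one would most expect chronic HCV to shift. The rule therefore tends to pick up consequences of the exposure.

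A regression that holds those consequences fixed estimates only the part of the HCV effect that does not pass through them or their correlates. That is a different quantity from the one in objective 1.2.2. In an observational comparison, readers will give weight to the adjusted estimate because it is the one that deals with confounding. The problem also spreads. Section 2.1 Background attributes lower hsCRP and lipids in HCV to impaired liver function, so a biomarker comparison adjusted for albumin or liver tests could remove the contrast it is meant to show.

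**Working it through.** **1. The plan's own power.** Section 9.3.1 gives: "RHI is expected then to be 1.6 in HIV/HCV and 1.3 in HIV, with standard deviation (SD) of 0.37". Only the size of the difference is used here. With 80 and 40 subjects, SE = 0.37 × √(1/80 + 1/40) = 0.37 × 0.1936 = 0.0717.

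- Difference 0.3: 0.3/0.0717 = 4.19; power 98.7% (normal) or 98.6% (noncentral t, 118 df). Stated: 99%.
- Difference 0.2: 0.2/0.0717 = 2.79; power 79.7% or 79.1%. Section 9.3.1 says: "if we conservatively estimate the difference in baseline RHI to be 0.2 between the 2 groups, we will have 80% power with this sample size".

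Both figures reproduce as a plain two-group comparison with no covariates. No stated number is wrong.

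**2. Would the rule select a consequence of HCV?** The documents define no threshold, so assume that a difference means p < 0.05. For a variable that HCV shifts by s within-group SDs, the noncentrality is s/√(1/80 + 1/40) = 5.16 × s.

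- s = 0.5: noncentrality 2.58, selected with probability about 73%.
- s = 1.0: noncentrality 5.16, selected with probability over 99%.

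The same rule also admits noise. Among 10 to 30 independent characteristics with no true difference, it selects 0.05 × 10 = 0.5 to 0.05 × 30 = 1.5 on average. The chance of at least one is 1 − 0.95^10 = 40% to 1 − 0.95^30 = 79%.

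**3. What adjustment would do to the estimate.** The documents give no mediated share and no shift, so these are assumptions. Let the true total difference be T = 0.2, let HCV shift one covariate by a SDs, and let a fraction f of T pass through it. A negative f means that the covariate path runs against the total effect. Then:

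- covariate slope b = f × T/a
- adjusted difference = T × (1 − f)
- residual variance = 0.37² − b²
- variance inflation = 1 + a² × (80 × 40/120)/118, which is 1.056 at a = 0.5 and 1.226 at a = 1.0
- power from the noncentral t with 117 df

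| Share f | Adjusted difference | Power, a = 0.5 | Power, a = 1.0 |
|---|---|---|---|
| 0 | 0.20 | 76.8% | 70.6% |
| 25% | 0.15 | 55.5% | 47.3% |
| 50% | 0.10 | 36.0% | 25.5% |
| −25% | 0.25 | 93.8% | 88.4% |

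For T = 0.3, the adjusted differences at f = 25%, 50% and −25% are 0.225, 0.15 and 0.375.

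**4. Reading the table.** The shift in the estimate is the issue, not the power. The losses in the f = 0 row are ordinary collinearity and would arise equally with a genuine confounder that separates the groups. Power need not fall when the estimate is wrong. At a = 0.3 and f = 50%, b = 0.333, the residual variance drops to 0.1369 − 0.1111 = 0.0258, and power is 88% although the estimate is halved to 0.10.

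**The case against.** Several points on the other side stand.

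- **The powered comparison is unadjusted.** The t-test or Wilcoxon comes first and the regression is additional. A reader might infer that the primary RHI comparison is itself biased. The documents do not support that: no covariate touches the unadjusted test. They also do not say which result is primary, which is a gap of its own.
- **The named covariates are not HCV consequences on their face.** They are PAT site, CD4 nadir and ART type. Section 9.4.1 lists patient characteristics apart from CVD biomarkers, HOMA-IR, haemoglobin A1c and FRS. Section 9.4.2 enters each biomarker in addition to the Aim 1 covariates. A fair reading keeps inflammation, lipids and HOMA-IR out. It does not keep out liver tests and platelets, which are not listed apart. Calling the covariates confounders shows intent, but the rule does not carry it out.
- **Some variables could not serve in the full cohort.** INR is collected only in coinfected subjects, A1c only in diabetic subjects, and fasting insulin and glucose only in non-diabetic subjects. Biopsy results are recorded only where available. The practical scope is mainly AST, ALT, bilirubin, albumin and platelets.
- **Bias toward zero is not established.** A reader might infer it from the pathways in Sections 1.1.1 and 2.1 Background. The same background says that HCV liver disease lowers hsCRP and lipids, so a path in the opposite direction is possible. The documents give no relation between liver tests and RHI.

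**Conclusion.** The point holds for the adjusted regression in Section 9.4.1 and for the analyses that reuse its covariates. The rule as written allows variables changed by HCV into a model meant to estimate the effect of HCV, and the study collects such variables in both groups. This is an error in the operative rule, not merely missing detail.

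Its size and direction cannot be obtained from the documents. The range of 0.10 to 0.25 for a true 0.2 rests wholly on assumed mediated shares of −25% to 50%. The power figures rest in addition on assumed shifts of 0.3 to 1.0 SD and a single covariate. They illustrate the problem and are not evidence of a loss. The stronger reading, that the primary test is attenuated and underpowered, is not supported. The matter should be corrected before the adjusted analysis is run.

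**What to change.** In Section 9.4.1, replace the open phrase with a closed, prespecified list: PAT site, the matching factors from Section 3.0 (with diabetes subject to the decision below), CD4 nadir, ART type, and any other collected factors judged not to be caused by HCV. Then:

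- State that liver tests, platelets, fibrosis and steatosis, lipids, HOMA-IR, A1c, the CVD biomarkers and FRS do not enter the total-effect model even if they differ between groups. They may appear only in a separate analysis labelled as a direct-effect analysis.
- Make an explicit decision on diabetes and give the reason. Section 3.0 makes it a matching factor, while Section 2.1 Background names it as a mechanism of HCV.
- State whether the unadjusted or the adjusted comparison is primary.
- Apply the same list to the biomarker comparisons. In Section 9.4.2, refer to the list rather than to whatever Aim 1 happened to select.

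The cost is SAP wording only, with no new data or subjects. The downside is that baseline differences in liver or metabolic variables will be described, not adjusted for, in the main model.

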1.2 Primary Objectives

- 1.2.1 To establish a UCLA CTSI-wide cohort of demographically diverse HIV/HCV coinfecting and matched HIV mono-infected men and women with HIV suppressed on stable antiretroviral therapy (ART).
- 1.2.2. To determine the effect of HCV coinfection on endothelial function in the HIV-1-infected cohort at baseline.
- 1.2.3 To assess whether non-hepatic biomarkers of endothelial dysfunction, inflammation, and thrombosis (sICAM-1, sE-selectin, Lp-PLA2, IL-6, and D-dimer) are better correlates of endothelial function than traditional hepatic-derived biomarkers (hsCRP and lipids) in HIV/HCV coinfecting in cross-sectional assessment at baseline.

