3.0 STUDY DESIGN

This is a prospective, observational, longitudinal study of two groups, Group A, HIV/HCV coinfecting subjects and Group B, HIV monoinfected subjects. The HIV/HCV subjects

will be frequency-matched to the HIV monoinfected subjects by age (<40, 40-49, 50-54, and ≥55 years), race (white, black, other), sex at birth, diabetes (yes/no), smoking status (current or not), HMG Co-A reductase inhibitor (statin) and hormonal therapy use, and CD4 cell count (200-349 and ≥350 cells/mm³) at baseline. All subjects will be followed for a minimum of 1 year. A subset of the HIV/HCV coinfecting group are expected to initiate HCV treatment during this time and will be followed through up to 24 weeks following end of HCV treatment. All subjects will be included in baseline cross-sectional analysis of endothelial function, measured by peripheral arterial tonometry (PAT) and laboratory testing for circulating CVD biomarkers. All subjects will have follow-up PAT and laboratory testing and clinical follow-up. Those HIV/HCV coinfecting that do not begin HCV treatment and all HIV monoinfected will have follow-up PAT and laboratory testing at 1 year. Those HIV/HCV coinfecting who begin HCV treatment will have follow-up PAT and laboratory testing at 4 weeks after end of HCV treatment, but will be followed clinically for up to 24 weeks after end of treatment to capture complete HCV treatment response data.

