Correlation analysis (Pearson or Spearman) will be conducted to evaluate the association of each circulating biomarker as the predictor and RHI as a continuous outcome variable. Further correlation of biomarkers with each other and with RHI will be performed by use of correlation matrices. Multiple linear regression models will be used while controlling for confounders as in Aim 1 analysis, but with each biomarker as the primary independent variable to determine the contribution of each biomarker as a predictor of RHI. A final model will be constructed by including all significant biomarkers to predict RHI. The adjusted R-squared value will be used to indicate the predictive ability of the model. Similar analysis will be carried out in HIV-monoinfected subjects only to derive the RHI prediction model. The models for each cohort will be compared to each other for their predictive ability and differences in individual biomarker

significance in each cohort. This analysis will allow us to define whether non-hepatically-derived biomarkers have stronger correlation with RHI than hepatically-derived biomarkers.

9.4.3 Objective: To determine the effect of HCV co-infection and HCV virologic suppression post treatment on endothelial function and CVD biomarkers in the HIV-1-infected cohort over one year of follow-up.

Change in RHI and change in biomarkers from baseline to follow-up will be compared among 4 groups of subjects (HCV treatment responders and non-responders, untreated HIV/HCV subjects, and HIV controls). Boxplots will be used to visually display the difference among 4 groups. Pair-wise comparison will be carried out based on 2-sample t-test or Wilcoxon test. ANCOVA will be carried out to compare among 4 groups adjusting for baseline values and demographic characteristics and other baseline confounders. Adjusted comparison between any 2 groups will be estimated based on appropriate contrast. Correlation analysis will be carried out between change in biomarkers and change in RHI.

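### The within-cohort marker-RHI regressions in 9.4.2 take their covariates from a between-cohort comparison, so matched risk factors such as age, smoking and statin use are left out to the extent that matching works

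*Combined protocol and SAP*

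**What the plan says.** Primary objective 1.2.3 asks whether five non-hepatic markers "are better correlates of endothelial function than traditional hepatic-derived biomarkers (hsCRP and lipids) in HIV/HCV coinfecting in cross-sectional assessment at baseline". Section 9.4.2 answers in three steps: unadjusted Pearson or Spearman correlations; regressions of RHI on each marker; and a final model holding every marker that reached significance, judged by adjusted R-squared. The steps are repeated in the HIV monoinfected cohort and the two cohorts' models are compared.

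For the regressions the covariate rule is: "Multiple linear regression models will be used while controlling for confounders as in Aim 1 analysis". No list follows. Aim 1 is taken here to mean 9.4.1, the first analysis objective, where RHI is compared between HIV/HCV and HIV, "adjusting for PAT performance site and any differences in baseline characteristics including CD4 nadir and ART type". The same section describes how baseline differences are examined: "ANOVA (analysis of variance) will be used to compare continuous variables by HCV status and site", with chi-square tests for categorical variables. It also sets the level: "All tests will be 2-sided and a p-value less than 0.05 will be considered statistically significant".

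Section 3.0 says that the HIV/HCV subjects are "frequency-matched to the HIV monoinfected subjects by age (<40, 40-49, 50-54, and ≥55 years" and by "race (white, black, other), sex at birth, diabetes (yes/no), smoking status (current or not), HMG Co-A reductase inhibitor (statin) and hormonal therapy use", and also by CD4 count.

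**The concern.** In 9.4.1 the exposure is HCV status, so a confounder has to differ between the cohorts, and adjusting for what differs is reasonable. In 9.4.2 the exposure is a marker level inside one cohort. A confounder there is anything related to both the marker and RHI among those subjects, whether or not its distribution matches that of the other cohort. Matching protects the first comparison and does nothing for the second.

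The borrowed rule therefore tends to drop the factors that the design treated as important enough to match on. At stake are the adjusted marker-RHI associations for a primary objective. Selection carries the problem forward: a marker that is significant only because it tracks age or smoking passes into the final model and adds to its adjusted R-squared.

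**Working it through.** **1. Which covariates enter.**

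| | 9.4.1 (Aim 1) | 9.4.2 regressions |
|---|---|---|
| Subjects | both cohorts | one cohort at a time |
| Exposure | HCV status | one marker |
| Covariates | PAT site; CD4 nadir and ART type (named); other baseline characteristics that differ | as in Aim 1 |

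No other section names age, smoking or statin use for the baseline marker models. Section 9.4.3 adjusts for demographic and other baseline confounders, but only in the four-group analysis of change. The Framingham score is described in 9.4.1 and is not a covariate in 9.4.2.

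**2. How often a matched factor would enter.** Section 9.4.1 does not define a difference. If it means a two-sided test at 0.05 with 80 and 40 subjects, a true standardised difference d is flagged with probability Φ(d/SE − 1.96) + Φ(−d/SE − 1.96), where SE = √(1/80 + 1/40) = 0.194.
- d = 0: 5%
- d = 0.2: d/SE = 1.03, giving 18%
- d = 0.3: d/SE = 1.55, giving 34%

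On that reading, modest residual imbalance would usually not bring a matched factor into the model.

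**3. Whether these factors can confound.** Section 2.1 (Background) supplies both links. It says PAT results correlate with known cardiovascular risk factors, and that the non-hepatic markers were consistently associated with classical risk factors. It also criticises earlier studies of adhesion molecules for not controlling traditional risk factors.

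**4. The plan's own figures.** Section 9.3.2 gives 80% power for r above 0.31 at n=80 and above 0.42 at n=40. By Fisher z, power = Φ(atanh(r)·√(n−3) − 1.96).
- n=80, r=0.31: 0.3205 × 8.775 − 1.96 = 0.853, power 80.3%.
- n=40, r=0.42: 0.4477 × 6.083 − 1.96 = 0.763, power 77.7% (noncentral t gives 81.4%).

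Both are reproduced within about two points. They refer to unadjusted correlations.

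**5. Size of the effect of one omitted factor.** Suppose a factor correlates a with the marker and a with RHI, and the marker has no relation to RHI of its own. The induced correlation is a². The documents give no value for a, so 0.2 to 0.4 is an assumption. Example at a = 0.3: r = 0.09, atanh(0.09) × √77 = 0.792, and Φ(0.792 − 1.96) + Φ(−0.792 − 1.96) = 12.4%. Simulation used 20,000 data sets per setting.

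| a | Induced r | n=80, Fisher z | n=80, simulated | n=80, factor in model | n=40, simulated |
|---|---|---|---|---|---|
| 0.2 | 0.04 | 6.4% | 6.6% | 5.3% | 5.5% |
| 0.3 | 0.09 | 12.4% | 12.6% | 5.1% | 8.7% |
| 0.4 | 0.16 | 29.4% | 29.2% | 4.7% | 16.8% |

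Entries are the chance of p<0.05 for a marker with no association of its own. For a binary factor held by 15–25% of subjects, such as statin use might be, an induced r of about 0.04 to 0.08 is a fairer assumption. The same formula gives about 6% to 11%.

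**The case against.** - **The objective asks for correlates, not causes.** A marker that follows RHI because it reflects age or smoking is still a correlate, and the Pearson or Spearman correlations that 9.3.2 powers are unadjusted by design. This stands for those correlations. It does not cover the regressions, which 9.4.2 says are there to control for confounders; once that is the purpose, the set has to suit the within-cohort question.
- **Omission is not certain.** PAT site is always included, CD4 nadir and ART type are named, and the wording on differences is open. Frequency matching on eight factors, with open-ended lowest and highest age bands, may leave imbalance that brings age, smoking or statin use in. This stands as a limit. But whether a confounder is controlled would then depend on how enrolment fell out.
- **The size rests on assumed strengths.** This stands in full. Smoking and statin use are binary, where the lower figures are more realistic. Excluding known cardiovascular disease and insulin-treated diabetes may also narrow the spread of risk.
- **The study is meant to generate preliminary data.** True, but 1.2.3 is listed as a primary objective and the correction costs little.

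**Conclusion.** The point holds for the 9.4.2 regressions and the final model built from them. The borrowed rule selects covariates on the wrong criterion, and nothing elsewhere in the plan corrects it. How much is lost depends on how well matching works and how strongly the omitted factors relate to marker and RHI. Under a single omitted factor at 0.2 to 0.4, the per-marker false-positive rate at n=80 is about 7% to 29%, with an induced correlation of 0.04 to 0.16 against a planned detectable 0.31.

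Three stronger readings are tempting and not supported:
- **That the correlations for 1.2.3 are confounded by this rule.** They carry no covariates under any version of it.
- **That the ranking of hepatic against non-hepatic markers is distorted, with statin use as the main cause.** The documents state no statin effect on lipids or hsCRP, and the calculation concerns one marker at a time, not a ranking.
- **That false positives would be very frequent.** At a = 0.5 the rate at n=80 would be about 62%, but nothing in the documents suggests a factor that strong.

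**What to change.** In 9.4.2, replace the reference to the Aim 1 confounders with a pre-specified set that enters whether or not it differs between cohorts and is the same for every marker: continuous age, sex, race, current smoking, diabetes, statin use and PAT site. Keep CD4 nadir and ART type in the HIV/HCV model. Hormonal therapy use and current CD4 count are also matched; the list leaves them out for economy, and the team can add them if it judges them relevant to marker and RHI.

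To compare the two cohorts' models, fit one smaller common core in both, for example age, sex, smoking, statin use and PAT site, so that a difference in adjusted R-squared does not come from different covariates. State that the Pearson or Spearman correlations remain unadjusted.

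Cost: wording only, since the protocol already records these items or matches on them. The full set uses 8 degrees of freedom (race takes 2, the others 1 each), or 10 with CD4 nadir and a two-category ART type, at n=80. The core set uses 5, which is noticeable at n=40.
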